Assess the effectiveness of different efficacious strategies to decrease the rate of major wound complications following abdominal surgery among high-risk individuals.

Hypotheses

1. Among high-risk patients undergoing abdominal surgery, the use of “small-bites” closure as opposed to “large-bites” closure will increase the proportion of patients who are free of major, chronic wound complications at 1-year post-operative.
2. Among high-risk patients undergoing abdominal surgery, the biologic tissue reinforcement of the suture line as opposed to no reinforcement will increase the proportion of patients who are free of major, chronic wound complications at 1-year post-operative.

Methods

This is a single-institution, 2x2 factorial randomized controlled trial assessing the effectiveness of known efficacious treatments (“small-bites” and tissue reinforcement) among high-risk patients undergoing midline laparotomy or laparoscopic-assisted surgery. [19] Laparoscopic-assisted abdominal surgery is defined as any surgery requiring an open incision in addition to laparoscopy to insert a hand (hand-assisted laparoscopy) or specimen extraction site ≥ 3 cm in

length. This length is chosen because any smaller incision will likely be closed with interrupted sutures rather than running sutures.

Table 1: 2x2 Factorial Design for Prevention of Major, Chronic Wound Complication [19]

		Randomization 1	
		Small-Bites	(Current Care) Large-Bites
Randomization 2	Mesh	Small-Bites Mesh	Large-Bites Mesh
	(Current Care) No Mesh	Small-Bites No Mesh	Large-Bites No Mesh

A 2x2 factorial trial design is utilized because it is more efficient (can assess two interventions simultaneously) and mimics real-world practice (e.g. adoption bundle therapies, adoption of multi-faceted interventions). In addition, the 2x2 factorial design remains novel, particularly among surgical literature that can improve profile of studies performed with this approach.

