Based upon prior studies, it is estimated that the risk of a major, chronic wound complication in this population is at least 30% while either intervention would result in a decrease in relative risk by 30% (i.e. absolute risk reduction from 30% to 20%). The risk of complication at 1 year is the same with open or laparoscopic assisted surgery as shown in multiple prior studies. [1,2,26] Assuming an alpha of 0.05, beta of 0.20, and a dropout rate of 20%, a total of 192 300 patients would need to be enrolled and 154 patients randomized. Based upon our current surgical volume of nearly 6000 general surgical procedures performed each year and our track record of enrolling over 400 surgical patients in the past year for three other trials, we anticipate completing enrollment within one year. To encourage patient follow-up, all patients will be provided with up to a \$10 gift card at the one-year follow-up and \$20 at the three-year follow-up along with payments for their parking (\$10) at both one- and three-year visits. [23]

The primary outcome will be assessed as a categorical variable using a chi square test. In addition, analysis will be performed using a Cochran-Mantel-Haenszel method as well as a multivariate regression analysis accounting for the 2 randomizations and the stratification. Secondary outcomes will be assessed either chi-square or Kruskal-Wallis test.

Based upon traditional Frequentist assessment, if the effect size does not achieve “statistical significance” the conclusions risk being reported as a false negative. To address this potential risk, a more real-world, realistic analysis will be performed using a Bayesian analysis will also be performed. [24,25] The Bayesian models will take the same form as the Frequentist models and include the same covariates. Posterior point estimates, credible intervals, and probability of increase in proportion of patients without hernias or complications will be calculated. Similar models will be used for secondary outcomes. **If interactions or modifiers are identified, then this study will be underpowered and should be considered a pilot study to appropriately power future multi-center randomized controlled trials.**

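### The planned effect is stated as two different targets: a 30% relative reduction (30% to 21%) and 30% to 20% (a one-third reduction), and the stated sample sizes follow from neither

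*Combined protocol and SAP*

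**What the plan says.** All the sizing inputs are in the first paragraph of the Statistical analysis section of the combined protocol and SAP.

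- Control risk: "the risk of a major, chronic wound complication in this population is at least 30"%.
- Effect in relative form: "either intervention would result in a decrease in relative risk by 30"%.
- Effect in absolute form, in a parenthesis that explains the relative form: "i.e. absolute risk reduction from 30% to 20"%. Read together, the two forms run "decrease in relative risk by 30% (i.e. absolute risk reduction from 30% to 20"%.
- Error rates and loss: "Assuming an alpha of 0.05, beta of 0.20, and a dropout rate of 20"%.
- Resulting size: "a total of 192 300 patients would need to be enrolled and 154 patients randomized". Two enrolment numbers stand side by side here. One may be a superseded figure whose deletion mark was lost, so both are examined below.

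The next paragraph gives the primary test: "The primary outcome will be assessed as a categorical variable using a chi square test". The Methods section gives the design: "This is a single-institution, 2x2 factorial randomized controlled trial". The plan does not state the sidedness of the test, the allocation ratio, the sample-size formula, or whether 20% or 21% was entered as the treated rate.

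**The concern.** The parenthesis presents the two forms as equivalent, and they are not. The sentence covers either intervention, so the ambiguity reaches both hypotheses of the factorial design.

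One point on the treated rate looks trivial. Required sample size, however, varies roughly with the inverse square of the difference, so going from 10 points to 9 adds about a quarter. The rates given are the more favourable of the two targets. A reader who takes the relative reduction as the planned effect and the 30% and 20% as its rates will think the trial has more power for that effect than it has. Until one target is fixed, neither the sample size nor the power can be checked or restated.

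**Working it through.** **Inputs from the Statistical analysis section.** Control risk 30%; treated risk 20% (absolute form) or 30% × (1 − 0.30) = 21% (relative form); alpha 0.05; power 0.80; dropout 20%.

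**Assumptions.** Two-sided test; 1:1 allocation; each factor compared at its margin, so half of the total is at each level; 30% taken as the risk at the control level of each margin.

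**Step 1: the two effects.**
- 30% relative reduction: 0.30 × 0.70 = 0.21, a difference of 9 points.
- 30% to 20%: (0.30 − 0.20)/0.30 = 0.333, a difference of 10 points.

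**Step 2: can the stated size be reproduced?** The pooled-variance formula per level, with p̄ the mean of p1 and p2, is

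n = [1.960 × √(2p̄(1 − p̄)) + 0.842 × √(p1(1 − p1) + p2(1 − p2))]² / (p1 − p2)²

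- 30% v 20%: [1.960 × √0.375 + 0.842 × √0.370]² / 0.10² = 293.2, so 294 per level. Total 588, or 588/0.8 = 735 enrolled.
- 30% v 21%: [1.960 × √0.37995 + 0.842 × √0.3759]² / 0.09² = 367.0, so 367 per level. Total 734, or 734/0.8 = 918 enrolled.
- Ratio: 734/588 = 1.25.

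The stated figures are not reproduced. Variants do not help. For 30% v 20% the total is 626 with a continuity correction, 582 with unpooled variance, 462 one-sided, and 502 one-sided with correction. For 30% v 21%, one-sided, it is 578. None is near 154, 192 or 300. The only link found among the stated numbers is dropout: 154/0.8 = 192.5.

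**Step 3: power at the stated sizes.** With n = total/2 per level,

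power = Φ{[(p1 − p2)√n − 1.960 × √(2p̄(1 − p̄))] / √(p1(1 − p1) + p2(1 − p2))}

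Example, 240 total (n = 120): for 30% v 20%, (0.10 × 10.954 − 1.200)/0.608 = −0.172, giving 43%. For 30% v 21%, (0.09 × 10.954 − 1.208)/0.613 = −0.362, giving 36%.

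| Evaluable total | Source | 30% v 20% | 30% v 21% |
|---|---|---|---|
| 154 | stated as randomized | 30% | 25% |
| 192 | one enrolment figure, no loss | 36% | 30% |
| 240 | 300 less 20% dropout | 43% | 36% |
| 300 | other enrolment figure, no loss | 52% | 43% |

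The choice of target moves power by about 5 to 8 points. Under either target, power is far below 80%.

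**Step 4: what the stated sizes would detect.** From a 30% control risk with 80% two-sided power: 154 patients detect about 30% v 11.8% (61% relative reduction), 192 about 30% v 13.4% (55%), 240 about 30% v 15.0% (50%), and 300 about 30% v 16.4% (45%). Neither 30% nor 33% is in that range.

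**The case against.** **It is only rounding.** The inputs are round estimates, the control risk is given as a floor, and the Background section cites 30% to 80% for such patients. One point on the treated rate is small beside that uncertainty. This may well explain how the sentence arose, and it is a good reason to rate the point as minor. It does not reconcile the text, because neither figure is marked as approximate and a reader cannot tell which was rounded.

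**The baseline may be higher.** A higher control risk lowers the requirement. At 60%, a one-third reduction needs 194 patients in total and a 30% reduction needs 240. But the parenthesis itself starts from 30%, and at 60% a 10-point reduction would need 776. The sentence as written does not describe a higher-baseline calculation.

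**The analysis does not use the target.** This stands. The chi-square, Cochran-Mantel-Haenszel, regression and Bayesian analyses do not depend on 20% or 21%, and no success threshold is tied to either. What is affected is the planned effect and its power, not the validity of the tests.

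**A stronger reading to avoid.** A reader might infer that the trial was sized on 30% v 20%, so that it has 80% power for the larger effect and loses some for the stated one. The documents do not support this. They do not say which rate was used, and no stated total follows from 30% v 20%. A trial with 588 evaluable patients appears nowhere in the plan, so there is no 80% power to lose. The figure 300 is close to the 294 needed per level for 30% v 20%, but the plan calls it a total. A per-level number used as a total is only a possibility.

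**Conclusion.** The inconsistency is certain: the sentence equates a 9-point and a 10-point reduction. The two targets differ by about 25% in required size (588 v 734) and by about 5 to 8 points of power at the sizes in the plan. The mismatch does not account for those sizes, which give about 25% to 52% power across the two targets against the claimed 80%.

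Taken alone, this is a minor error in the planned effect, possibly from rounding. It still needs correcting, because power for the primary outcome cannot be restated until one target is chosen.

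The contradiction needs no assumption. The sizes and powers rest on a two-sided test, 1:1 allocation, comparison at each margin and a 30% control-level risk. A one-sided test lowers the requirements to 462 and 578, still far above the stated sizes. If the other factor also works, the marginal rates fall and the requirements rise to 744 (25% v 16.7%) and 910 (25.5% v 17.85%).

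**What to change.** In the Statistical analysis section, state one target: either a one-third relative reduction (30% to 20%, 10 points) or a 30% relative reduction (30% to 21%, 9 points).

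Then replace the claimed 80% power with the power that the stated sample size gives for that target. State which enrolment figure applies, the number expected to be evaluable after dropout, the sidedness, the allocation ratio and the formula. Under the assumptions above, the sentence would report about 30% or 25% power at 154 evaluable patients, and about 43% or 36% at 240.

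The cost is a sentence or two and a less favourable power figure. Eligibility, treatment, follow-up and the planned tests do not change. Choosing the target without restating the power would remove the contradiction but leave an 80% claim that neither target supports.

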Tissue Reinforcement of Incisional Closure Among High Risk Patients

NCT03148496

[figure not shown]
Version Date: 03/06/2020

IRB NUMBER: HSC-MS-17-0063
IRB APPROVAL DATE: 03/06/2020

Tissue Reinforcement of Incisional Closure Among High Risk Patients

[name], [name], [name]
Mentor: [name]

Background

One-third of all individuals will undergo abdominal surgery in their lifetime. [1,2] Following abdominal surgery, 30% of patients will suffer a major chronic complication with their wound closure in the first post-operative year. This may include significant wound infections, open wounds, fluid collections, fascial dehiscence, or incisional hernia. These complications not only have a substantial impact on the health care system (cost and chronic disease) and the hospital (cost and space), but most importantly have a substantial impact on the patient. Major chronic wound complications adversely impact patient quality of life and function. [3-6]

Patients at greatest risk for major wound complications include comorbid patients such those who are overweight or obese, currently smoke or have COPD, are immunosuppressed, are malnourished, or who have evidence of contamination (wound classes 2-4). Among these patients, the risk of developing a major wound complication ranges from 30%-80%. [1,2,7,8,9]

Potential methods to reduce major wound complications include utilizing specific suturing techniques or reinforcing the incision line. Suturing technique of small-bites (0.5x0.5 cm bites) as opposed to large bites (1.0x1.0 cm bites) has been shown to be efficacious in European populations with a typical body mass index of 20-25 kg/m². [10-12] Tissue reinforcement has been shown to decrease rates of major wound complications in small randomized controlled trials. [13-18]

However, the lack of widespread adoption of these practices may be due to issues of generalizability including strict inclusion criteria, careful patient selection, and small study size. For example, the generalizability of small bites to an overweight population (mean BMI in the United States is 28 kg/m²) as opposed to a normal-weight population are unclear. [10-12] The use of synthetic materials in comorbid patients or complex settings may risk major wound complications such as prosthetic infection. Biologic materials have been shown to be effective in decreasing major wound complications but in different settings. [13-19]

Specific Aims

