1 month	Routine care	Routine care Clinical exam Assessing: Hernia (clinical) Dindo-clavien complications Surgical site infections Patient centered outcomes (modified Activities Assessment Scale and Euroqol-5D)	\$0
1 year	Research follow-up	Clinical exam Assessing: Hernia (clinical and ultrasound) Dindo-clavien complications Patient centered outcomes (modified Activities Assessment Scale and Euroqol-5D)	\$10 gift card \$10 parking
3 years	Research follow-up	Clinical exam Assessing: Hernia (clinical and ultrasound) Dindo-clavien complications Patient centered outcomes (modified Activities Assessment Scale and Euroqol-5D)	\$20 gift card \$10 parking

A trained surgical clinician blinded to the treatment arms will collect outcomes. A blinded outcomes adjudication committee (non-participating members of the Ventral Hernia Outcomes Collaborative) will verify the primary outcome.

A Data Safety Monitoring Board of the Ventral Hernia Outcomes Collaborative will be developed. All major complications (Dindo-Clavien 3-5) including deaths, reoperations, mesh explantations, and enterocutaneous fistulas will be reviewed. No interim analysis will be planned as analysis of the primary outcome will weaken the strength of the results. Safety and stopping points will be determined based upon clinical judgment or greater than 50% rate of major complications.

Enrollment will occur prior to the operation either in the clinic (for elective cases) or on the day of surgery (for urgent or emergent cases). The randomization schema will be variable block randomization with blocks stratified by surgical approach (laparoscopic versus open): this is chosen not because there is belief that there will be a difference in outcomes, but because it is a different surgical approach and should be balanced. Allocation will occur at the time of abdominal closure by phone call to the study office.

Statistical analysis

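### The stated 80% power for a fall from 30% to 20% fails at every listed sample size: it needs 588 evaluable patients, and 300 enrolled with 20% lost gives about 43%

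*Combined protocol and SAP*

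**What the plan says.** The trial is a single-institution 2x2 factorial (Methods, Table 1) with two hypotheses: small against large bites, and biologic mesh against no mesh. The primary outcome is binary at one year, and the first-named test is chi-square.

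The Statistical analysis section puts the risk at 30% or more and expects either intervention to give a "decrease in relative risk by 30% (i.e. absolute risk reduction from 30% to 20" per cent. The size follows from "Assuming an alpha of 0.05" and "beta of 0.20, and a dropout rate of 20%, a total of 192 300 patients would need to be enrolled and 154 patients randomized". The figures 192 and 300 stand side by side and may be old and new text run together; that is not counted as an error here.

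Two later statements bear on power. The Bayesian analysis is justified because, without statistical significance, "the conclusions risk being reported as a false negative". The section then ends: "If interactions or modifiers are identified, then this study will be underpowered and should be considered a pilot study".

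On timing, Methods says "Allocation will occur at the time of abdominal closure by phone call to the study office", so randomization comes at the end of the operation and the primary outcome a year later.

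**The concern.** The power statement is the only justification for the sample size, and it covers both hypotheses. Detecting a 10-point difference from 30% ordinarily takes several hundred patients per group, so 154, 192 and 300 in total all look too small. If the claim is wrong, each hypothesis is more likely to be missed than detected at 240 evaluable, even if the expected effect is real. A reader who trusts the 80% would then take a non-significant result as fair evidence against small bites or mesh.

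The closing caveat adds to this. It ties lack of power to the discovery of interactions or modifiers. Beside a stated beta of 0.20, it implies that the main effects are adequately powered otherwise.

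**Working it through.** **Inputs from the Statistical analysis section:** alpha 0.05; power 0.80; rates 0.30 and 0.20; dropout 20%; sizes 192, 300 and 154. **Assumptions, because the text is silent:** two-sided test (a chi-square test is two-sided by construction), 1:1 allocation in each randomization, and each main effect tested on the full factorial margin. Comparing single cells would use half as many patients.

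**1. Reproducing the plan's figures.** 192 x 0.8 = 153.6, so 192 and 154 are linked through the dropout rate. 300 x 0.8 = 240, so 154 does not belong with 300. No two-group formula gives any of the three. A one-sample test of 20% against a fixed 30% gives [1.960 x sqrt(0.21) + 0.842 x sqrt(0.16)]² / 0.10² = 152.5, so 153, and 153 / 0.8 = 191.25, so 192. That may be where the figures came from, but the document names no formula, and a one-sample test does not apply to two randomized groups.

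**2. Size needed.** Per margin, with p̄ = (p1 + p2)/2:

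n = [1.960 x sqrt(2p̄(1−p̄)) + 0.842 x sqrt(p1(1−p1) + p2(1−p2))]² / (p1−p2)²

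For 0.30 v 0.20: [1.960 x sqrt(0.375) + 0.842 x sqrt(0.37)]² / 0.01 = (1.200 + 0.512)² / 0.01 = 293.2, so 294. The total is 588 evaluable, and 588 / 0.8 = 735 enrolled. Other formulas give 582 (unpooled), 584 (arcsine) and 626 (continuity-corrected). One-sided, the total is 462.

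**3. Power at the listed sizes.** Power = Φ{[sqrt(n) x (p1−p2) − 1.960 x sqrt(2p̄(1−p̄))] / sqrt(p1(1−p1) + p2(1−p2))}. At 240, n = 120: (1.095 − 1.200) / 0.608 = −0.172, and Φ = 0.432. Exact enumeration of the chi-square test gives 0.434.

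| Evaluable | 30% v 20%, two-sided | 30% v 20%, one-sided | 30% v 21%, two-sided |
|---|---|---|---|
| 154 | 29.8% | 41.6% | 24.7% |
| 192 | 35.9% | 48.2% | 29.7% |
| 240 (300 less 20%) | 43.2% | 55.8% | 35.9% |
| 300 | 51.6% | 64.0% | 43.1% |
| 588 | 80.1% | 87.8% | 70.8% |

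With 80% power (two-sided) from 30%, the detectable rate is about 11.8% at 154, 15.0% at 240 and 16.4% at 300.

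**4. Relative against absolute reduction.** (30 − 20) / 30 = 33%. A 30% reduction gives 0.7 x 30 = 21%, which needs 734 evaluable and 918 enrolled.

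**5. Meaning of the 30%.** The text does not say whether 30% is the rate on the control margin or in the large-bites, no-mesh cell. If it is the cell rate and both interventions work:

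- Multiplicative effects (relative risk 2/3 each): margins (30 + 20)/2 = 25% and (20 + 13.3)/2 = 16.7%. This needs 744; power is 35.5% at 240 and 42.7% at 300.
- Additive effects (10 points each): margins 25% and (20 + 10)/2 = 15%. This needs 500; power is 49.1% at 240 and 58.2% at 300.

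**6. Timing of the loss.** If 192 and 154 are the current pair, the whole 20% is spent between enrolment and randomization, and nothing is left for loss by one year. Losing 20% of 154 leaves about 123 and power of about 25%.

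**The case against.** Five points can be made for the plan.

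- **The 43% is conditional.** It assumes that 300 is current, that 240 are evaluable and that 30% is the control-margin rate. This stands, and the figure should always carry those conditions. The alternatives run from about 30% (154 evaluable) to 58% (additive effects, 300 evaluable). Stacking additive effects, a one-sided test and no loss at 300 gives [sqrt(150) x 0.10 − 1.645 x sqrt(0.32)] / sqrt(0.315) = 0.52, or about 70%. No reading reaches 80%.
- **The base rate is a floor.** The section says the risk may exceed 30%, and Background gives 30% to 80% for such patients. At relative risk 2/3, 80% power needs a control-margin rate of about 54% at 240 or 47% at 300; at 0.7, about 60% or 53%. Those rates lie within the range, but the plan's calculation uses 30%.
- **The effect size may be the outdated input.** 30% v 15% needs 240.9 evaluable, and 240.9 / 0.8 is about 301, close to 300. This may be coincidence. If it is the origin of 300, the stated effect is wrong instead of the power, and the paragraph still needs correcting.
- **The caveat does not say the main effects are otherwise well powered.** True in the letter; the implication comes from the stated beta. The Bayesian analysis also softens the harm by giving posterior estimates and credible intervals, but it does not make the power claim true.
- **33% against 30% may be rounding.** Possibly, but the evaluable number needed moves from 588 to 734.

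**Conclusion.** The concern holds. At the plan's own alpha, power and rates, 588 evaluable patients are needed, about twice the largest listed figure. With 300 enrolled and 20% lost, each hypothesis has about 43% power for 30% v 20% on the margin, and what 240 patients can detect with 80% power is roughly a halving of risk, not a reduction by a third. The result assumes 1:1 allocation and full-margin comparisons; the failure to reach 80% does not depend on sidedness, on which of 154, 192 or 300 is current, or on how the 30% is read. The mismatch of relative and absolute reduction and the interaction-only caveat are lesser faults in the same section. This must be corrected, because nothing else in the document supports the sample size.

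**What to change.** Revise the sample-size paragraph and the closing caveat:

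1. Give one set of enrolled, randomized and evaluable numbers, with the 20% loss taken after randomization. If 300 is current and all are randomized, that is 300 / 300 / 240.
2. Say whether 30% is the control-margin rate or the current-care cell rate, then give the one power figure that matches. At 240 evaluable for an expected 10-point fall: about 43% on the margin reading; on the cell reading, about 36% (multiplicative) or 49% (additive). Alternatively, state the effect detectable with 80% power: 30% to about 15% on the margin. If 300 came from other inputs, state them.
3. Make the reductions agree: 30% to 20% is 33%; a 30% reduction is 30% to 21%.
4. Reword the caveat so that limited power is acknowledged for the main effects, whether or not interactions are found.

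Optionally, say that a non-significant result will be read from its confidence interval beside the Bayesian estimates. At 240 the 95% half-width is 1.96 x sqrt((0.21 + 0.16)/120), about 11 percentage points.

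The cost is one paragraph and one sentence, and a less favourable power statement. No extra patients, visits or data are needed.

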Primary outcome will be proportion of patients at one year with a major chronic wound complication. Major chronic wound complications will include any persistent wound or infection at 1-year post-operative, fascial dehiscence, or fascial defect. Persistent wound or infection will include any enterocutaneous fistula, open wound, or symptomatic fluid collection. Fascial dehiscence or fascial defect will be defined as any defect noted on clinical assessment. Clinical assessment is clinical examination and demand-driven CT scan ordered based upon signs or symptoms including patient complaint of pain, bulge by patient report or physical exam, or wound complication. This represents current practice.[21] In addition, all patients will undergo

an ultrasound performed by a trained clinician to assess for any chronic, major wound complications at one year post-operative. Patients will also be followed for up to three years post-operative.

Secondary outcomes will include any Dindo-Clavien complications, surgical site infections, reoperations, operative duration, patient centered outcomes, surgeon perceptions, and cost analyses. Dindo-Clavien and surgical site infections have been defined.[20,22] Reoperation will be defined as any unplanned invasive procedure involving the fascia, mesh, or peritoneal cavity. Patient centered outcome based upon the modified Activities Assessment Scale and Euroqol-5D will be measured at 1 year and 3 years. Surgeon perceptions will include Likert type and open-ended questions assessing perception, barriers, and likelihood of utilizing the interventions outside of the trial. Cost will be calculated from the hospital's perspective by assessing charges for all patient visits, admissions, and procedures. These charges will be adjusted utilizing department-specific cost-to-charge ratios (CCR). The CCR are the ratios at the cost center level that hospitals are required to submit to Centers for Medicare and Medicaid Services annually (under the hospital's annual Medicare cost report). This will allow charges to be converted to cost by applying these CCRs to charges. Following state-of-the-art guidelines, cost will be discounted at an annual rate of 3%. The robustness of the results will be assessed by performing sensitivity analyses of plausible ranges for the project parameters and probabilistic sensitivity analysis. Follow-up schedule is provided in Table 2.

Table 2: Follow-up Schedule

Timing	Level of Care	Assessments	Reimbursements

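### The 154 patients randomized do not follow from 300 enrolled and a 20% dropout, and read literally the plan states no allowance for loss before the one-year outcome

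*Combined protocol and SAP*

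**What the plan says.** The sample-size paragraph under Statistical analysis sets its terms as "Assuming an alpha of 0.05, beta of 0.20, and a dropout rate of 20"%, for a fall in complication risk from 30% to 20%. It concludes that "a total of 192 300 patients would need to be enrolled and 154 patients randomized".

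The enrollment paragraph at the end of Methods makes enrolled and randomized two separate events. On the first: "Enrollment will occur prior to the operation either in the clinic (for elective cases) or on the day of surgery", the latter for urgent or emergent cases. On the second: "Allocation will occur at the time of abdominal closure by phone call to the study office".

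The outcome paragraph in Methods fixes the endpoint well after both: "Primary outcome will be proportion of patients at one year with a major chronic wound complication".

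The plan gives no number of patients expected to be evaluable at one year, and no second loss rate. The nearest it comes is to exclude patients unlikely to be followed for a year (Methods) and to pay patients who return (Statistical analysis).

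**The concern.** A sample-size statement should let the reader go from patients consented, to patients allocated, to patients with a primary outcome. Here the chain breaks in two places.

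- **The counts do not agree.** The stated dropout links 154 to 192, not to 300. If 300 replaced 192, then 154 was either left behind or should have gone with it.
- **The allowance sits at the wrong step, on the literal reading.** The step from enrolled to randomized covers only consented patients who are never allocated at closure. Loss in the following year is what removes patients from the primary comparison, and on that reading nothing is set aside for it.

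At stake is what the trial is expected to deliver. Any power or precision restated for it depends on how many patients reach one year with an outcome, and the paragraph does not settle that number.

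**Working it through.** **Inputs.** From Statistical analysis: control risk 30% (given as a minimum), intervention risk 20%, alpha 0.05, dropout 20%, a chi-square test, and the counts 192, 300 and 154. From Methods: the times of enrollment, allocation and outcome. Assumed, because not stated: a two-sided test, and 1:1 allocation on each factorial margin, so that each level has n = N/2.

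**Step 1. Reproduce the plan's pair.** 192 × 0.80 = 153.6, which rounds to 154. In reverse, 154/0.80 = 192.5. So 192 and 154 are linked by exactly one 20% loss.

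**Step 2. Try the current enrollment figure.** 300 × 0.80 = 240, not 154. Going from 300 to 154 would be a loss of 1 − 154/300 = 48.7%, which the plan does not state.

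**Step 3. Place the loss in time.** Enrolled is before surgery, randomized is at closure, and the outcome is one year later. As worded, the 20% is used up between the first two. The interval between the second and third has no figure.

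**Step 4. Evaluable counts under each reading.**
- All 300 enrolled are allocated and 20% are lost by one year: 300 × 0.80 = 240.
- 20% of the 300 are not allocated and 20% of the rest are lost: 300 × 0.80 × 0.80 = 192. Using the 20% twice is an assumption.
- 154 is the evaluable number: 154.
- 154 are randomized and a further 20% are lost: 154 × 0.80 = 123.2, about 123. This too uses the 20% twice, and is an assumption.

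**Step 5. Power and precision at each count.** Pooled-variance two-proportion test:

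power = Φ{[0.10 × √n − 1.96 × √(2 × 0.25 × 0.75)] / √(0.30 × 0.70 + 0.20 × 0.80)}

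For N = 240, n = 120: (1.0954 − 1.2002)/0.6083 = −0.172, and Φ(−0.172) = 0.432.

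The 95% confidence-interval half-width for the risk difference is 1.96 × √(0.37/n). For n = 120 this is 10.9 points.

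| Evaluable N | Power, 30% v 20% | Half-width (points) |
|---|---|---|
| 240 | 43% | 10.9 |
| 192 | 36% | 12.2 |
| 154 | 30% | 13.6 |
| 123 | 25% | 15.2 |

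The plan's 30% relative reduction taken literally gives 0.30 × 0.70 = 21%, not 20%. Against 21%, the four powers are about 36%, 30%, 25% and 21%.

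**Step 6. Context.** For 80% power at 30% v 20%, n = [1.96 × √(2 × 0.25 × 0.75) + 0.842 × √0.37]² / 0.10², which gives 294 per level, or 588 evaluable. None of the counts above comes near this.

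**The case against.** The strongest reply has several parts.

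- **The 154 may not be current text.** The document reads like a tracked-changes copy: two enrollment figures stand side by side, and the reference list carries doubled numbers. If the clause giving 154 was struck out together with 192, the mismatch disappears. That stands as a possibility which the extracted text cannot settle. For the same reason, the two adjacent enrollment figures are not in themselves an error in the plan. But no replacement for 154 is printed, and if it was deleted the plan then gives no randomized or evaluable count at all.
- **Dropout may mean loss to follow-up, with randomized a slip for evaluable.** The payments for returning, in the same paragraph, fit that reading. It would supply the one-year allowance for 192. It is not what the sentence says, and 154 would still not match 300.
- **300 enrolled and 154 randomized can coexist.** They can, if about 49% are never allocated. The plan states 20%.

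A reader might also go further than the documents allow:

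- That the plan prints two contradictory randomization targets. It prints one, 154; the 240 is derived from 300 and the 20%.
- That 123 is the expected number evaluable. It needs a second 20% loss that the plan does not state.
- That allocation will stop at 154. No rule ties the end of allocation to a count of randomized patients; the text speaks only of completing enrollment.

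Finally, power is well under 80% on every reading, so resolving this sentence does not repair the sample size. That is correct. It remains a separate correction because a revised power statement needs one agreed evaluable count.

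**Conclusion.** The point holds in a limited form. As printed, 154 follows from 192 and not from 300, so it does not fit the current enrollment figure and appears not to have been updated. On the literal wording, the only 20% falls before allocation, and no allowance is stated for loss before the primary outcome. Whether the sponsor intended that is unknown; if evaluable was meant, the allowance exists and only the mismatch with 300 remains.

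The size is a spread from 123 to 240 evaluable patients, with power of about 25% to 43% and half-widths of 15.2 to 10.9 points. The two ends belong to different readings and should not be taken as sampling uncertainty. The figures rest on the plan's 30% and 20%, a two-sided 0.05 test and assumed 1:1 margins; the counts of 192 and 123 also rest on applying the 20% twice.

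**What to change.** Remove or correct 154, and replace the sentence with one chain that starts from the 300 enrolled:

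1. the number expected to be allocated at closure, with any loss before allocation stated as its own rate;
2. the number expected to be evaluable at one year, with the 20% explicitly assigned to loss after randomization.

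Then quote power and confidence-interval width at the evaluable count, in place of the 80% implied by the stated beta. If all 300 are allocated and 20% are lost, that is 240 evaluable, about 43% power and a half-width of 10.9 points. If 20% are also lost before allocation, it is 192, about 36% and 12.2 points.

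The 300 should not simply be relabelled as the number randomized. If any consented patients are not allocated, that needs more than 300 enrolled; with a 20% loss before allocation, 300/0.80 = 375.

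The cost is one rewritten sentence and no patients beyond the 300 already stated. The reported power becomes less favourable. Make the change together with the correction of the power statement, since it does not bring the trial to 80%.
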